5.1 Imputation rules

Throughout the study reasonable attempts will be made to limit the amount of missing data. However missing data will not be imputed, unless imputation is needed to perform specific analyses (e.g., for a dose administration record (DAR) with missing end date or end date after the cut-off date, the cut-off last contact date needs to be imputed as an end date to allow for calculation of treatment exposure duration and dose intensity). If it is required to impute an end date, the imputed date will be displayed and flagged in the appropriate listing, if produced. Imputation rules for missing dates (if applied) will be defined in the PDS before the database lock.

5.1.1 Study drug

The default rule for missing/partial start date or end date of study drug imputation is the following:

- Day missing will be replaced by 15;
- Day & month missing will be replaced by 1 July;
- No imputation if day, month and year are missing.

Imputed dates will not be displayed in listings except when required.

In the situation where the event date is partial or missing, the date will appear partial or missing in the listings, and study day, and any corresponding durations will be presented based on the imputations specified in the following paragraphs of this section.

5.1.2 AE date imputation

Missing or partial AE dates will not be imputed.

5.1.3 Concomitant medication date imputation

5.1.3.1 Prior therapies date imputation

In order to define prior medications/therapies, missing or partial start and stop dates will be handled as described in [Section 5.1.1](#).

5.1.3.2 Post therapies date imputation

In order to define post/concomitant medications/therapies, missing or partial start and stop dates will be handled as described in [Section 5.1.1](#).

5.1.3.3 Other imputations

Imputation of missing or partial dates for medical/disease history will be handled as described in [Section 5.1.1](#).

Partial date imputation is allowed for event (death)/censoring coming from ‘Death information’ eCRF.

For rare cases when either day is missing or both month and day are missing for the date of death, the following imputation rules will be implemented:

- If only day is missing, then date of death is imputed as max [(1 mmm-yyyy), min(last contact date +1, cutoff date)].
- If both day and month are missing, then date of death is imputed as max [(1 Jan-yyyy), min (last contact date +1, cutoff date)].

5.2 AEs coding/grading

Adverse events are coded using the latest version of Medical Dictionary for Regulatory Activities (MedDRA) terminology.

AEs will be assessed according to the Common Terminology Criteria for Adverse Events (CTCAE) version 4.03.

The CTCAE represents a comprehensive grading system for reporting the acute and late effects of cancer treatments. CTCAE v4.03 grading is by definition a 5-point scale generally corresponding to mild, moderate, severe, life threatening, and death.

If CTCAE grading does not exist for an adverse event, grades 1 – 4 corresponding to the severity of mild, moderate, severe, and life-threatening will be used. CTCAE grade 5 (death) will not be used in this study; if an AE results in death it will be documented in the outcome (“fatal”). Information on deaths will also be collected on the ‘Death’ CRF.

5.3 Laboratory parameters derivations

CTC grades for laboratory values in Novartis Oncology (based on CTCAE v4.03 – Month YEAR)

Table for CTCAE v4.03

5.4 Statistical models

5.4.1 Analysis supporting primary objective(s)

Not Applicable.

5.4.2 Analysis supporting secondary objective(s)

Not Applicable.

5.5 Rule of exclusion criteria of analysis sets

Table 5-1 Protocol deviations that cause subjects to be excluded

Deviation ID	Description of deviation	Exclusion in analyses	Severity Code
IC01	Participant is an adult \geq 18 years old at the time of consent	Include in all analyses	49
IC02	Participant with ABC (loco-regionally recurrent or metastatic) not amenable to curative therapy.	Include in all analyses	49
IC03	Participant with a histologically and/or cytologically confirmed diagnosis of ER-positive and/or PR-positive breast cancer by local laboratory.	Include in all analyses	49
IC04	Participant with a confirmed HER2-negative ABC (see Protocol definition)	Include in all analyses	49
IC05	Participant with a pathology report confirming PIK3CA mutant status by a certified laboratory using a validated PIK3CA mutation assay (from either tissue or blood).	Include in all analyses	49
IC06	Participant had progression of disease during or after endocrine-based therapy	Include in all analyses	49
IC07	Participant has a Performance Status at screening and at Cycle 1, Day 1 visit lower than or equal to 1 (ECOG/WHO PS \leq 1)	Include in all analyses	49
IC08	Participant has adequate bone marrow and organ function as defined in the following laboratory valued (as assessed by site laboratory for eligibility) - see protocol	Include in all analyses	49
IC09	Participant is a man or a pre- or post-menopausal woman (for Pre and Post-menopausal see Protocol definition)	Include in all analyses	49
IC10	Participant is willing to operate a smartphone including the telemedicine application and a medical device (glucometer)	Exclude from all analyses	8
IC11	Participant is willing to follow the requirements for remote participation	Exclude from all analyses	8
IC12	Participant has signed ICF before any trial related activities and according to local guidelines.	Exclude from all analyses	8
E01	Participant has received prior treatment with any PI3K, mTOR, or AKT inhibitor.	Include in all analyses	49

E02	Participant with known hypersensitivity to alpelisib or fulvestrant, or to any of the excipients of alpelisib or fulvestrant.	Include in all analyses	49
E03	Participant has had major surgery within 14 days prior to trial treatment start and/or has not recovered from major side effects.	Include in all analyses	49
E04	Participant with inflammatory breast cancer at screening.	Include in all analyses	49
E05	Participant with an established diagnosis of diabetes mellitus type I or not controlled type II (based on fasting glucose [FG] and HbA1c, see inclusion criterion 8)	Include in all analyses	49
E06	Participant with impairment of gastrointestinal function or gastrointestinal disease that may significantly alter the absorption of the trial treatments (e.g., ulcerative diseases, uncontrolled nausea, vomiting, diarrhea, malabsorption syndrome, or small bowel resection) based on investigator discretion.	Include in all analyses	49
E07	Participant has currently documented pneumonitis/interstitial lung disease (the chest Computerized Tomography (CT) scan performed at baseline for the purpose of tumor assessment should be reviewed to confirm that there are no relevant pulmonary complications present).	Include in all analyses	49
E08	Participant with Child Pugh score B or C.	Include in all analyses	49
E09	Participant with uncontrolled hypertension defined by a Systolic Blood Pressure \geq 160 mmHg and/or Diastolic Blood Pressure \geq 100 mmHg, with or without antihypertensive medication. Initiation or adjustment of antihypertensive medication(s) is allowed prior to screening.	Include in all analyses	49
E10	Participant with clinically significant, uncontrolled heart disease and/or recent cardiac events (see Protocol version 01 for definition)	Include in all analyses	49
E11	Participant with any other concurrent severe and/or uncontrolled medical condition that would, in the investigator's judgment, contraindicate participant participation in the clinical trial (e.g., chronic active hepatitis, [testing not mandatory unless required by local regulations or requirements] confirmed pneumonitis etc.).	Include in all analyses	49
E12	Participant is currently receiving any of the following medications and cannot be discontinued 7 days prior to the start of the treatment: - Strong cytochrome P (CYP)3A4 inducers	Include in all analyses	49

	- Inhibitors of breast cancer resistance protein (BCRP)		
E13	Participant has a history of acute pancreatitis within 1 year of screening or past medical history of chronic pancreatitis.	Include in all analyses	49
E14	Participant with unresolved osteonecrosis of the jaw.	Include in all analyses	49
E15	Participant has a history of severe cutaneous reactions like Stevens-Johnson-Syndrome, Erythema Multiforme, or Toxic Epidermal Necrolysis, or Drug Reaction with Eosinophilia and Systemic Symptoms.	Include in all analyses	49
E16	Participant with evidence of disease progression during the pre-trial induction therapy and prior to first dose of alpelisib	Include in all analyses	49
E17	Participant has received radiotherapy ≤ 4 weeks or limited field radiation for palliation ≤ 2 weeks prior to trial treatment initiation, and who has not recovered to grade 1 or better from related side effects of such therapy (with the exception of alopecia).	Include in all analyses	49
E18	Participant is currently receiving or has received systemic corticosteroids ≤ 2 weeks prior to starting trial treatment, or who have not fully recovered from side effects of such treatment. (see Protocol for definition)	Include in all analyses	49
E19	Participant participated in a prior investigational study within 30 days prior to the start of trial treatment or within 5 half-lives of the trial treatment, whichever is longer.	Include in all analyses	49
E20	Participant has not recovered from all toxicities related to prior anticancer therapies to NCI CTCAE version 4.03 Grade ≤ 1. Exception to this criterion: participants with any grade of alopecia are allowed to enter the trial.	Include in all analyses	49
E21	Participant has a concurrent malignancy or malignancy within 3 years of start of trial treatment, with the exception of adequately treated, basal or squamous cell carcinoma, nonmelanomatous skin cancer, or curatively resected cervical cancer	Include in all analyses	49
E22	Participant has central nervous system (CNS) involvement which was not previously treated and not fulfilling the following 3 criteria to be eligible for the trial: - Completed prior therapy (including radiation and/or surgery) for CNS metastases ≥ 28 days prior to the start of trial entry and - CNS tumor is clinically stable at the time of screening and	Include in all analyses	49

	- Participant is not receiving steroids and/or enzyme inducing anti-epileptic medications for brain metastases.		
E23	Participant has a known history of Human Immunodeficiency Virus infection (testing not mandatory unless required by local regulations or requirements).	Include in all analyses	49
E24	Participant is not able to understand and to comply with trial instructions and requirements, including oral administration of trial treatment	Exclude from all analyses	8
E25	Participant is a nursing (lactating) or pregnant woman as confirmed by a positive serum (hCG) test prior to initiating trial treatment	Include in all analyses	49
E26	Participant is a woman of child-bearing potential defined as all women physiologically capable of becoming pregnant, unless they are using highly effective methods of contraception during trial treatment and at least for 2 years after the last dose of any trial treatment. Highly effective contraception methods include: see Protocol definition	Include in all analyses	49
E27	Participant is a sexually active male unwilling to use a condom during intercourse while taking trial treatment, and for 2 years after the last dose of trial treatment. A condom is required for all sexually active male participants to prevent them from fathering a child AND to prevent delivery of trial treatment via seminal fluid to their partner. In addition, male participants must not donate sperm during the trial and up to the time period specified above	Include in all analyses	49
E28	Participants with active infections, including a COVID-19-related diagnosis	Include in all analyses	49
S1	Study medication not administered	Exclude from safety analyses	5
O1	Study drug related toxicity triggering a dose modification, as per protocol, and participant receives the incorrect dose	Include in all analyses	49
O2	Study drug related toxicity triggering a dose interruption, as per protocol and participant not discontinued from treatment	Include in all analyses	49
O3	Participant concomitantly administered with a strong inducer of CYP3A or inhibitors of BCRP, as per protocol	Include in all analyses	49
O4	Missed questionnaires or e-diary, as per protocol	Include in all analyses	49

Table 5-2 Code Text

Code	Code text
5	Exclude from safety analyses

8	Exclude from all analyses
49	Include in all analyses

6 Reference

Fayers PM (2001). Interpreting quality of life data: population-based reference data for the EORTC QLQ-C30. *Eur J Cancer*; 37(11):1331-4.

ICH E9(R1) Harmonized Guideline: addendum on estimands and sensitivity analysis in clinical trials to the guideline on statistical principles for clinical trials. Final version on 20 November 2019.

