12.1 Analysis sets

The Full Analysis Set (FAS) comprises all participants that received any trial treatment.

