2.2 Analysis sets

Enrolled Set: The enrolled set consists of all patients who signed the informed consent.

Full Analysis Set: The Full Analysis Set (FAS) consists of all enrolled set patients who received at least one dose of any component of study treatment.

Safety Set: The Safety Set consists of all enrolled set patients who received at least one dose of any component of study treatment and have at least one post-baseline safety assessment.

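### SAP Table 5-1 removes from all analyses some treated participants whom the FAS and Safety Set definitions include, and the SAP declares no change from the protocol

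*SAP*

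**What the plan says.** **The sets.** Protocol 12.1 has one analysis set: "The Full Analysis Set (FAS) comprises all participants that received any trial treatment". SAP 2.2 starts from consent: "The enrolled set consists of all patients who signed the informed consent". Its FAS is the Enrolled Set members who had at least one dose of any treatment component. Its Safety Set adds one further condition, at least one post-baseline safety assessment. No definition mentions eligibility or protocol deviations, and none refers to SAP 5.5.

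**The exclusion codes.** SAP 5.5, Table 5-1, assigns each deviation a code, and Table 5-2 explains the codes. Code 8 is "Exclude from all analyses", code 5 is "Exclude from safety analyses", and code 49 keeps the participant in everything. Four rows have code 8:

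- IC10, willingness to operate the smartphone, application and glucometer
- IC11, "Participant is willing to follow the requirements for remote participation"
- IC12, "Participant has signed ICF before any trial related activities and according to local guidelines"
- E24, "Participant is not able to understand and to comply with trial instructions and requirements, including oral administration of trial treatment"

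Code 5 is used once, for S1 (study medication not given). Every other row has code 49.

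**The link between the two.** SAP 2.3.4 plans a listing of deviations that lead to exclusion from the FAS and the Safety Set, so the codes are meant to act on these sets. SAP 4, the place for changes to protocol-specified analyses, reads not applicable.

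**The concern.** The same participant can be inside a set by its definition and outside it by Table 5-1, and nothing in the SAP says which rule prevails. Suppose a participant signs consent in time, is dosed, has a post-baseline safety assessment, and is then found to have been unwilling at entry to use the telemedicine application. SAP 2.2 puts this person in the FAS and the Safety Set. Table 5-1 takes the person out of both.

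Two things are at stake. The first is safety reporting: SAP 2.6 ties all safety outputs to the Safety Set, so code 8 would remove a treated participant's adverse events. The second is selection. IC10, IC11 and E24 concern willingness or ability to work with the remote procedures, which lies close to the primary objective (satisfaction with the decentralized approach). Removing such participants is not neutral for that question.

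**Working it through.** There is no planned figure to reproduce. The check sets the rules side by side and then bounds the effect of one exclusion.

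**Step 1. Apply each rule to a dosed participant with one code-8 deviation.**

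| Deviation | Protocol 12.1 FAS | SAP 2.2 FAS | SAP 2.2 Safety Set | Table 5-1 |
|---|---|---|---|---|
| IC10, IC11 or E24, valid consent | in | in | in, if assessed after baseline | out of everything |
| IC12, signed but late | in | in (the Enrolled Set has no timing condition) | in, if assessed after baseline | out of everything |
| IC12, never signed | in | out | out | out of everything |

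The first two rows conflict with both documents' definitions. The third conflicts only with the protocol FAS.

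**Step 2. Outputs reached by code 8.**

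- FAS: the primary-objective section (SAP 2.4), progression-free survival (SAP 2.5.2) and patient-reported outcomes (SAP 2.9).
- Safety Set: all safety outputs (SAP 2.6), including the adverse event counts and percentages in SAP 2.6.1 and 2.6.1.1.
- Enrolled Set: disposition (SAP 2.3.1) and the visit listings (SAP 2.5.1), because the code says all analyses.

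**Step 3. Compare with the other rows.** A dosed participant without a confirmed PIK3CA mutation (IC05), with prior PI3K, mTOR or AKT inhibitor treatment (E01), or pregnant at entry (E25) has code 49 and stays in everything. So does one with missed questionnaires or diary entries (O4). Table 5-1 therefore does not apply a general rule that ineligible participants are dropped.

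**Step 4. Size of one exclusion.** Let k of n participants have an event, with p = k/n.

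- Remove one with the event: (k − 1)/(n − 1) − k/n = −(1 − p)/(n − 1).
- Remove one without it: k/(n − 1) − k/n = +p/(n − 1).
- The first is largest at k = 1 and the second at k = n − 1. Both extremes equal 1/n in absolute size.

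At the planned n = 20 the bound is 1/20 = 5.0 points (1/20 to 0/19, or 19/20 to 19/19). As a typical case, take the SOLAR-1 hyperglycemia rate of 63.7% from Protocol 1.1. Then 0.637 × 20 = 12.7, about 13, and 13/20 = 65.0%.

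- Excluded participant had the event: 12/19 = 63.2%, a shift of −1.8 points.
- Excluded participant did not: 13/19 = 68.4%, a shift of +3.4 points.

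The number dosed is not given. If it were 10 (an assumption), the bound would be 1/10 = 10 points; if 5 (also an assumption), 1/5 = 20 points.

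**The case against.** The best defence is that SAP 5.5 supplements SAP 2.2. Its heading announces exclusion rules for the analysis sets, and SAP 2.3.4 expects such exclusions. On that reading, the fault within the SAP is mainly a missing cross-reference. This is fair as far as it goes. It does not explain why the result is narrower than the protocol FAS while SAP 4 reports no change, and it gives no reason to drop a treated participant's adverse events.

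A second defence is that willingness to take part remotely matters for the decentralized-trial endpoints, so separate coding has a purpose. Some rationale exists there, including for the objective on safe remote management. It is weak for general adverse event reporting. Stating the exclusion in SAP 2.2 and declaring it in SAP 4 would also make the documents consistent, but treated participants would still be missing from the safety outputs.

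The third defence is practical, and it largely stands. Protocol 5 and 8.1.1 require eligibility to be checked before treatment, and Protocol 8.6.2 has participants agree at enrollment to the remote arrangements. SAP 1 says the trial ended early and data will only be listed.

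A reader might infer more than the documents support:

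- *That participants were in fact excluded, or results biased.* No such deviation is documented.
- *That anyone who later gives up remote participation is dropped under IC11.* IC11 is an entry criterion. Protocol 3 and SAP 1.1 say that leaving remote participation is not a reason to leave the trial.
- *That exclusions could carry the six-month retention result across its 75% descriptive target.* Under assumed counts this is possible (14/20 = 70.0% becomes 14/18 = 77.8% if two non-remote participants are removed). However, SAP 2.5.1 now specifies only listings, with no retention proportion, so no planned output stands behind it.
- *That the data would vanish from the listings.* This is unclear. SAP 2.1 promises all collected data, and SAP 2.6 all safety events and assessments, while SAP 2.6 and 2.9 tie outputs to the sets.

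**Conclusion.** The conflict is real and should be corrected. Four code-8 rows in Table 5-1 exclude participants whom Protocol 12.1 includes. For IC10, IC11, E24 and a late-signing IC12 case, SAP 2.2 includes them too. The SAP does not declare the departure. For IC10, IC11 and E24, applying the code to safety is not justified by anything in the documents. IC12 is different, because a consent ground can be defended, but it has the same clash and needs to be stated.

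Severity is minor. The effect is at most 1/n per excluded participant, with n the denominator before that removal, in any percentage still produced. The 5-point figure assumes the planned 20 were dosed, so in a trial stopped for low enrollment it is an illustration only. It also assumes that the adverse event summaries in SAP 2.6.1 survive the listings-only statement in SAP 1. If no participant has one of these deviations, no output changes.

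**What to change.** 1. In SAP Table 5-1, recode IC10, IC11 and E24 from 8 to 49 and flag these cases in the deviation listing. No dosed participant with valid consent is then removed from the FAS or the Safety Set for these deviations.
2. If code 8 is kept for IC12 on consent grounds, state it in SAP 2.2 for all three sets, for example: *Participants with deviation IC12 are excluded from the Enrolled Set, the FAS and the Safety Set.* The Enrolled Set must be named because its definition has no condition on when consent was signed and code 8 reaches its outputs as well.
3. Record the IC12 exception in SAP 4 as a departure from Protocol 12.1.

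The cost is SAP wording only: three codes, one sentence in section 2.2 and one line in section 4. No new data are needed. The downside is that a rare ineligible participant stays in the outputs, visibly flagged.
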